7.2 Rationale

The ABBVIE REGIMEN ± RBV for the treatment of CHC has been shown to be safe and effective in randomized controlled clinical trials with strict inclusion and exclusion criteria under well controlled conditions.

The ABBVIE REGIMEN is expected to be first available in Poland for the treatment of CHC in 2015.

The rationale for this observational study is to determine how the efficacy and safety of the ABBVIE REGIMEN as demonstrated in pivotal trials translates into real world everyday clinical settings, evaluating its effectiveness. Whereas efficacy can be defined as a measure of the capacity of a treatment to produce the desired effect in a controlled environment, such as in a randomized controlled trial, effectiveness is ‘the extent to which a drug achieves its intended effect in the usual clinical setting’ [64]. Effectiveness trials typically have limited exclusion criteria and will involve the broader patient populations in routine clinical practice, treated per local label, which might include patients with heterogenous compliance patterns and patients with significant comorbid conditions and could be used to model and disseminate best practices. Effectiveness research allows for external patient-, provider-, and system-level factors and can therefore be relevant for health-care decisions by both providers in practice and policy-makers [65].

This observational study is the first effectiveness research examining the ABBVIE REGIMEN ± RBV, used according to local label, under real world conditions in Poland in clinical practice patient population.

During the last decade when dual therapy with pegIFN plus RBV was standard of care for the treatment of CHC, management of patients and clinical outcome were improved following the discovery of predictive factors of virological response, often in observational studies with large data bases [66]. Thus treatment could be targeted to patients most likely to respond and futile treatment stopped in patients with a low likelihood of virological cure. HCV genotype and subtype, baseline viral load, fibrosis stage, age, treatment exposure and on-treatment virological response proved to be useful predictors for the eradication of HCV in everyday clinical practice [27]. More recently the discovery of a genetic disposition of the Interleukin 28B (IL28B) single nucleotide polymorphism (SNP) contributed further to our understanding of virological responses to treatment [67]. For new interferon-free treatment regimens knowledge of predictive factors of virological response is extremely sparse and several of the now well established predictors of response were not initially identified through analyses of the development trials. This observational study may play an important part in bridging the data gaps and could help identify predictive factors of virological response in everyday clinical settings which were not detected in interventional trials and which could be used to further optimize treatment with the interferon-free ABBVIE REGIMEN in the future.

The label of the ABBVIE REGIMEN will vary according to HCV genotype/subtype and stage of liver disease. It is therefore relevant to understand the pattern of use and outcome in daily clinical practice. In addition, this study will provide data on the impact

Confidential Information

No use or disclose outside AbbVie is permitted without prior written authorization from AbbVie

of adherence on treatment outcomes in everyday settings, which may help treating physicians to improve the management of patients under their care.

The aim of this observational study is to provide evidence of the effectiveness and patient reported outcome (PRO) about quality of life and work productivity during treatment with ABBVIE REGIMEN ± RBV in a real world setting across clinical practice patient populations.

8.0 Research Question and Objectives

8.1 Research Question

What is the effectiveness and patient reported outcome about quality of life and work productivity during treatment with interferon-free ABBVIE REGIMEN ± RBV in patients with CHC in a real life setting across clinical practice patient populations?

8.2 Objectives

8.2.1 Primary Objective

1. To describe in routine clinical practice the effectiveness of the interferon-free ABBVIE REGIMEN ± RBV in patients with CHC as evidenced by SVR12

8.2.2 Secondary Objectives

2. To provide real world evidence for predictive factors of virological response
3. To describe the pattern of real world use of the ABBVIE REGIMEN ± RBV with respect to different patient and treatment characteristics
4. To evaluate the influence of adherence on treatment outcome in routine clinical practice
5. To collect information on co-morbidities and concomitant medication in the Polish population
6. To describe the tolerability of the ABBVIE REGIMEN ± RBV

Confidential Information

7. To document the effect of the ABBVIE REGIMEN ± RBV on PROs and work productivity in the Polish population

9.0 Research Methods

9.1 Study Design

This is a prospective, multi-center observational study in patients receiving the interferon-free ABBVIE REGIMEN with or without RBV. The prescription of a treatment regimen is at the discretion of the physician in accordance with local clinical practice and label, is made independently from this observational study and precedes the decision to offer the patient the opportunity to participate in this study.

Adult patients chronically infected with HCV, receiving the interferon-free ABBVIE REGIMEN will be offered the opportunity to participate in this study during a routine clinical visit at the participating sites.

[figure not shown]
After written patient authorization has been obtained, patient data including demographic data, HCV disease characteristics, co-morbidities, co-medication, treatment details, and laboratory assessments as recorded in the patient's medical records (source documentation) will be documented in the electronic case report form (eCRF). Patients will be observed for the duration of the ABBVIE REGIMEN therapy and for up to 24 weeks after treatment completion. No patient identifiable information will be captured, a unique patient number will be automatically allocated by the web based eCRF system once the investigator or designee creates a new patient file.

This study is focusing on collecting real-world data. Follow-up visits, treatment, procedures and diagnostic methods will follow physicians' routine clinical practice. The observational study period entails the following data collection schemes, data documented will be those closest to the time windows as indicated in Figure 1:

- 12-week treatment regimen: four visits plus two interim data collection windows
- 24-week treatment regimen: four visits plus three interim data collection windows

This schedule is based on the anticipated regular follow-up for patients undergoing treatment for CHC.

Figure 1 - Study Flowchart

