9.2.1 Target Population

Patients are eligible for observation in this cohort if the following applies:

- Treatment-naïve or -experienced adult male or female patients with confirmed CHC, genotype 1 or 4, receiving combination therapy with the interferon-free ABBVIE REGIMEN ± RBV according to standard of care and in line with the current local label
- If RBV is co-administered with the ABBVIE REGIMEN, it has been prescribed in line with the current local label (with special attention to contraception requirements and contraindication during pregnancy)
- Patients must voluntarily sign and date a patient authorization to use and/or disclose his/her anonymized health data prior to inclusion into the study
- Patient must not be participating or intending to participate in a concurrent interventional therapeutic trial

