9.2.2 Study Duration

This is a prospective, observational study. The inclusion period will be approximately 6 months and the observational period of the study will be from baseline visit until 24 weeks post-treatment.

Confidential Information

The observational period for patients receiving 12 weeks of ABBVIE REGIMEN will be max. 36 weeks (12 weeks treatment and 24 weeks post-treatment observation) and for patients receiving 24 weeks of ABBVIE REGIMEN the observational period will be max. 48 weeks (24 weeks treatment and 24 weeks post-treatment observation).

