9.4.1.3 Post-Treatment Documentation

Follow-up visits are scheduled by the physician per routine clinical practice. Likewise treatment, procedures and diagnostic methods will follow physicians' routine clinical practice.

The following will be documented:

- Laboratory data

- Key clinical chemistry

- ALT
 - AST

- Remarks

- including ULN
including ULN,
APRI and FIB-4, will be calculated

- γ -GT
 - Total bilirubin
 - Albumin
 - Creatinine

- creatinine clearance will be calculated

- Key hematology

- Hb
 - Platelets
 - Prothrombin time

- or INR

- Virology

- HCV RNA

- quantitative/ qualitative HCV RNA PCR test, see 9.4.1.4

- HIV-infected patients only

- CD 4 count
 - HIV RNA

- most recent assessment
in copies/mL

- Tolerability (sAEs, see 0) and pregnancies (see 0)
- Patient questionnaires see 9.4.1.6

Confidential Information

No use or disclose outside AbbVie is permitted without prior written authorization from AbbVie

Table 2 - Data Documentation Schedule

Assessment/ Procedure (only available data to be collected; no diagnostic or monitoring procedures to be applied to the patients apart from those of routine clinical practice)	Baseline	Treatment Period			Post-treatment (PT) Period		
		On-treatment visits	Mid treatment visit for pts receiving 24 weeks of therapy	EoT ^b	Early PT visit	SVR 12 visit	SVR 24 visit
Patient authorization	X ^a						
Demographic information	X						
IL28B	X						
Relevant CHC disease characteristics	X						
Liver fibrosis stage	X						
CHC treatment history	X						
HCV genotype and subtype	X						
HCV RNA samples	X	X	X	X	X	X	X
Clinical chemistry and hematology	X	X	X	X	X	X	X
ABBVIE REGIMEN initiation documentation	X						
ABBVIE REGIMEN adherence		X	X	X			
Concomitant medication	X	X	X	X			
Relevant medical history, co-morbidities	X						
sAE, AE and pregnancy reporting	X	X	X	X	X ^c	X ^d	X ^d
For patients receiving RBV: Evidence, in accordance with local label, that female patient or female partner of male patient is not pregnant	X						
Patient questionnaires – WPAI, EQ5D-5L	X			X		X	X

Abbreviations: EoT = End of Treatment (at Week 12 or 24 or at premature discontinuation), PT = Post-Treatment

- a Written patient authorization must be obtained before any data documentation in the eCRF
- b Patients who prematurely discontinue should return to the site to document EoT data
- c Tolerability documentation until PT week 4
- d Pregnancy reporting for patients treated with DAA plus RBV

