11.1.4 Serious Adverse Event Collection Period

SAEs will be reported to AbbVie from the time the physician obtains the patient's authorization to use and disclose information until 30 days or 5 half-lives following the intake of the last dose of physician-prescribed treatment.

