#### **Target Population [TP]**

Patients will be included if the following applies:

- Age at least 18 years
- Confirmed CHC with genotype 1 and/or 4 only, receiving combination therapy with the interferon-free ABBVIE REGIMEN ± RBV. The prescribed ABBVIE REGIMEN needs to be known.
- Have voluntarily signed and dated a patient authorization to use prior to inclusion into the study
- Must not be participating or intending to participate in a concurrent interventional therapeutic trial

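### Enrolment at baseline is implied but not enforced, and the SAP does not identify patients authorized after the first dose, so SVR12 could be biased upward by an amount that the planned tables would not show

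*Protocol*

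**What the plan says.** **Who may enter, and when.** Protocol 9.2.1 admits patients "receiving combination therapy with the interferon-free ABBVIE REGIMEN ± RBV according to standard of care and in line with the current local label". Under section 9.1, adults "receiving the interferon-free ABBVIE REGIMEN will be offered the opportunity to participate in this study during a routine clinical visit", and the prescription "precedes the decision to offer the patient the opportunity to participate in this study". It ties the offer to the prescription and does not mention the first dose.

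**Authorization.** Protocol 9.2.1: "Patients must voluntarily sign and date a patient authorization to use and/or disclose his/her anonymized health data prior to inclusion into the study". SAP 4.2.1 (Target Population) repeats the condition: "Have voluntarily signed and dated a patient authorization to use prior to inclusion into the study". Footnote a to protocol Table 2 adds: "Written patient authorization must be obtained before any data documentation in the eCRF".

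**Signs that baseline enrolment is intended.**
- Table 2 marks authorization in the Baseline column only.
- Protocol 9.2.2 says that "the observational period of the study will be from baseline visit until 24 weeks post-treatment".
- Protocol 9.3.2 places the first EQ-5D-5L and WPAI before treatment starts.
- SAP 4.2.5 lists never having begun therapy among the reasons for not completing the study.

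**Analysis sets.** The target, core, sufficient-follow-up and safety populations in SAP 4.2.1 contain no condition on authorization date relative to first dose.

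**Safety.** Protocol 11.1.4: "SAEs will be reported to AbbVie from the time the physician obtains the patient's authorization to use and disclose information". Protocol 9.7.6 and SAP 4.2.8.3 count treatment-emergent events from the start of study drug.

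**The concern.** The primary result is a single uncontrolled percentage. Under protocol 9.7.1 and SAP 4.2.3, a patient with no usable SVR12 value after imputation counts as a failure. SAP 4.2.7.2.1 lists on-treatment virologic failure, death and premature discontinuation among the non-response categories. A starter who meets one of these early is a core-population failure if authorized on day 1. The same starter is absent from the data if the site would have made the offer only at a later visit. Late entry therefore removes failures and keeps successes, and the confidence interval does not reflect it.

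Protocol 9.9 discusses the direction of bias in SVR only for missing HCV RNA, which pulls the rate down. A reader would not learn that a bias in the other direction is possible.

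Two secondary results share the gap. A late entrant sits in the safety denominator from first dose although SAE reporting starts at authorization. The SAP's baseline windows (its Tables 3 and 4) cover HCV RNA and safety laboratory data but not the questionnaires, so no stated rule stops an on-treatment questionnaire from serving as the PRO baseline.

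**Working it through.** **1. The planned precision reproduces.** Protocol 9.5 expects 90% to 95% of 400 patients to be evaluable: 0.90 × 400 = 360 and 0.95 × 400 = 380. The Clopper-Pearson limits for 324 of 360 (90%) are 86.43% to 92.90%, a width of 6.47 points; Table 3 states 86.4, 92.9 and 6.5. The half-width is 6.47 / 2 ≈ 3.2 points.

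**2. Formula for the shift.** Let S be the true SVR12 rate among all starters, f the share of enrolled patients who enter late, and q the share of starters who have failed or left before the late-enrolment visit. If every one of those early losses would have been an SVR12 failure, the rate among late entrants is S/(1 − q). Then:

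- expected observed rate = (1 − f)·S + f·S/(1 − q)
- shift = f·[S/(1 − q) − S]

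**3. Inputs.** S = 90% is the planning value in protocol 9.5. The documents give no value for f. For q, protocol 7.1 says only that discontinuation in phase III was low. Both f and q are therefore assumptions, shown as a range.

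**4. Results at S = 90%, in percentage points.**

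| Early loss q | f = 10% | f = 25% | f = 50% |
|---|---|---|---|
| 1% | 0.09 | 0.23 | 0.45 |
| 2% | 0.18 | 0.46 | 0.92 |
| 5% | 0.47 | 1.18 | 2.37 |

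Example: q = 5%, f = 50% gives 0.50 × (0.90/0.95 − 0.90) = 0.50 × 0.0474 = 2.37 points.

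**5. Why these are upper values for the given f and q.** Protocol 9.2.3 provides for SVR12 data in patients who stop early with a virological response, so not every early leaver is a failure. Relapse and missing SVR12 data arise after treatment, so enrolment during treatment does not screen them out. At S = 90%, all non-response together is 10%; q = 5% would place half of it before the enrolment visit.

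**6. Safety windows side by side.** SAE reporting opens at authorization; the treatment-emergent window opens at first dose. For a late entrant these differ by the time already on treatment. Protocol 9.4.1 takes data from charts where available, so earlier events might be recorded retrospectively. No passage requires this or rules it out, so no figure is given for this part.

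**The case against.** The strongest reply is that the documents do describe baseline enrolment. Authorization is scheduled at baseline, beside the documentation of treatment initiation. The EQ-5D-5L and WPAI ask about today and the past seven days, so they cannot be reconstructed from a chart. Observation covers the full treatment course, the study is called prospective, and there is a disposition reason for patients who never began therapy. Someone receiving the regimen may simply be someone to whom it has been prescribed. The study flowchart (Figure 1) is not reproduced in the text available for this review and may add timing detail.

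This stands as evidence of intent. A reader might infer from the eligibility wording that nothing links authorization to the start of treatment, or that the design plans to enrol patients mid-course and so does raise SVR12 and lower adverse-event rates. The documents do not support that: mid-course entry is permitted by the wording, not planned, and any bias depends on whether it happens.

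A reader might also infer pressure to recruit patients already on treatment, because the March 2016 amendment raised the target from 100 to 400 while protocol 9.5 still gives a 6-month inclusion period. No passage makes that link. The interim rule in SAP 4.2.9, restricted to treatment starts before 1 April 2016, suggests that later starts were expected.

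What the reply does not supply is a control. Table 2 collects only available data, and a patient who enters late and lacks a pre-treatment questionnaire still meets every population definition and is analysed like any other.

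**Conclusion.** The point holds in conditional form. The schedule implies authorization at baseline, the eligibility criteria do not require it, and the SAP cannot show whether it happened. If patients were authorized after the first dose, SVR12 in the core population tends to be biased upward.

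The size cannot be determined from the documents. Under the assumed ranges for late entry and early loss, and with every early loss counted as a failure, the shift is at most about 0.1 to 2.4 points at 90% SVR12. Every value is below the planned half-width of about 3.2 points, though the top of the range is not negligible beside it. The safety part is weaker: earlier SAEs in late entrants may be missed unless taken from charts, and the documents are silent on this. It should not be read as a demonstrated lowering of adverse-event rates.

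This is a cheap improvement that protects an uncontrolled primary estimate, not a defect that undermines the study.

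**What to change.** - **SAP 4.2.1:** derive a flag from authorization date against first-dose date. Report the number of patients authorized after day 1 and how late they were.
- **SAP 4.2.7.1 and the related tables:** as a sensitivity analysis, repeat SVR12, the treatment-emergent adverse-event tables and PRO change from baseline in patients authorized on or before day 1. If nobody entered late, the count alone settles the matter.
- **Protocol 9.2.1, for patients still to be enrolled:** require authorization on or before the first dose, in line with Table 2.

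**Cost.** One derived variable and repeats of existing tables. The authorization form is signed and dated, but the documents do not list that date as an eCRF field, so it may have to be added from the form.

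The restricted set is smaller. Scaling the 6.47-point width by 1/√(1 − f) gives about 6.47/√0.90 = 6.8 points if 10% entered late and 6.47/√0.75 = 7.5 if 25% did. The loss of precision is modest unless late entry was common, and in that case the comparison is most needed.

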9.2 Setting

For overall research design and observational documentation schedule refer to Sections 9.1 and 9.4.1 as well as to Figure 1.

9.2.1 Target Population

Patients are eligible for observation in this cohort if the following applies:

- Treatment-naïve or -experienced adult male or female patients with confirmed CHC, genotype 1 or 4, receiving combination therapy with the interferon-free ABBVIE REGIMEN ± RBV according to standard of care and in line with the current local label
- If RBV is co-administered with the ABBVIE REGIMEN, it has been prescribed in line with the current local label (with special attention to contraception requirements and contraindication during pregnancy)
- Patients must voluntarily sign and date a patient authorization to use and/or disclose his/her anonymized health data prior to inclusion into the study
- Patient must not be participating or intending to participate in a concurrent interventional therapeutic trial

9.2.2 Study Duration

This is a prospective, observational study. The inclusion period will be approximately 6 months and the observational period of the study will be from baseline visit until 24 weeks post-treatment.

Confidential Information

The observational period for patients receiving 12 weeks of ABBVIE REGIMEN will be max. 36 weeks (12 weeks treatment and 24 weeks post-treatment observation) and for patients receiving 24 weeks of ABBVIE REGIMEN the observational period will be max. 48 weeks (24 weeks treatment and 24 weeks post-treatment observation).

9.2.3 Termination Criteria

For patients who terminate the ABBVIE REGIMEN prematurely for whatever reason the EoT eCRF page should be filled in and the reason for treatment discontinuation should be documented. If the reason for ABBVIE REGIMEN discontinuation is due to an SAE, the event must be reported to AbbVie within 24 hours of physician awareness (see Section 0).

If, in such patients, there is evidence of virological response during therapy or at EoT, the SVR12 and SVR24 pages should be completed if respective data is available.

9.2.4 Investigator Selection Criteria

University centers and outpatient clinics qualified by training and experience in the management of patients with CHC will be selected to participate in this study. The AbbVie Affiliate Medical Director will ensure that sites participating in the study are representative of the medical practice in the country, have the ability to conduct the study and their availability of the target patient population. The type of the participating treating institute will be documented in the eCRF.

9.3 Variables

9.3.1 Primary Variable

- The percentage of patients achieving SVR12 (HCV RNA <50 IU/mL 12 weeks [i.e. ≥70 days] after the last actual dose of the ABBVIE REGIMEN)

9.3.2 Secondary Variables

- Type of treatment regimen (± Dasabuvir, ± RBV, intended and actual combination, dose and duration)
- Adherence
 - Percentage of the DAA dose taken in relation to the target dose of DAA (cumulative dose taken divided by target dose in percent)
 - Percentage of the RBV dose taken in relation to the target dose of RBV (cumulative dose taken divided by target dose in percent)

Confidential Information

- Percentage of missed RBV treatment days in relation to the target number of RBV treatment days
- Co-morbidities and concomitant medication
- Serious and non-serious adverse events and pregnancy occurrences
- Questionnaires on PROs: e.g. EuroQol 5 dimension 5 level (EQ-5D-5L) questionnaire and work productivity and activity impairment (WPAI) questionnaire prior to treatment initiation, at EoT as well as 12 and 24 weeks after EoT

